19.1 Laboratory methods

IgG Fc glycosylation (sialylation and agalactosylation) will be measured with an immunoassay technique using lectins (a class of proteins, mostly from plants, which bind to specific sugars) (Wong et al., 2016). In order to investigate glycosylation patterns in more detail we will a subset of IVIG treated patients with the greatest change in glycosylation profile (n=10) and analyse samples by ultra-high performance liquid chromatography-mass spectrometry, as we have done previously, to give a more detailed picture of IgG Fc structure and shed light on potential interactions with the Fc gamma receptor ([name] will lead these studies) (Blundell, Le, Allen, Watanabe, & [name], 2017).

Inflammatory responses will be measured across a range of host mediators, including cytokines, transcripts and proteins. Cytokine analysis (via bead array) is already established in Liverpool (Michael, [name], Granerod, Brown, Davies, et al., 2016; Michael, [name], Granerod, Brown, Keir, et al., 2016). In addition, by measuring blood mRNA (via sequencing or targeted PCR) we will look for other host mediators that distinguish IVIG responders from non-responders, which will allow us to stratify treatment in the future, building on our earlier host transcriptomic studies ([name] et al., 2005; Hemingway et al., 2017). We have recently shown for another inflammatory brain condition (meningitis) that as few as four host genes may be used to distinguish those who respond to treatment (antibiotics) from those who do not (patent No. GB1606537.7 filed 14th April 2016; lead, [name]). Biomarkers of brain damage (such as neuro-filaments (NFL), Tau protein and S100B) will be measured in CSF (and serum) via ELISA in Liverpool and/or UCL. Novel auto-immune antibodies will be searched for using techniques established in the [name] group at Oxford. CSF will also be saved for exploratory proteomic studies, to be funded separately ([name] et al., 2010; [name], Fukushima, Yazaki, & Vincent, 2007; Michael, [name], Granerod, Brown, Davies, et al., 2016).

19.2 Mechanistic studies sample size

In a recent study of the effect of IVIG on sialylation of IgG Fc in chronic inflammatory demyelinating polyneuropathy (Wong et al., 2016), IVIG treatment resulted in a 68% increase in IgG Fc sialylation. Including samples from 228 randomised patients will provide 90% power with a two-sided 5% alpha to detect an absolute mean difference of approximately 5.7 x10^3 mm^2 Optic Density on western blot (assuming a mean glycosylation of 22 x10^3 mm^2 Optic Density Units in the placebo arm, a common standard deviation of 13.3, and 20% of participants not providing samples at 3-months). This translates into a 26% relative difference. Assuming 30% of these participants will be antibody positive (i.e. n = 68), we will have 90% power with a two-sided 5% alpha to detect an absolute mean difference of approximately 10.6 units within this sub-group, which translates into a 48% relative difference. We would look to further increase power by including baseline glycosylation as a covariate in the analyses. These sample sizes and analytical approaches would also allow further exploration within sub-groups (e.g. anti-neuronal antibody titres and inflammatory markers).

19.3 Statistical analysis of mechanistic studies

We will use independent samples t-tests to compare mean glycosylation at study entry between patients with autoimmune encephalitis and controls. We will repeat this analysis comparing patients that are antibody positive against controls.

Our main statistical analysis will compare mean glycosylation levels at 3-months between trial arms using analysis of covariance, with baseline glycosylation levels included as a covariate. Extending this analysis, we will consider subgroup analyses by antibody status, antibody titres, and inflammatory markers to understand the moderating effects of these variables.

We will explore the extent to which the effect of IVIG on clinical outcome at 12 months is mediated through glycosylation at 3 months. We will pre-specify in full our hypothesised pathways following discussion among the research team (including clinicians, basic scientists, statisticians, and patient-representatives). These pathways will be illustrated using a Directed Acyclic Graph. Using the g-computation formula, we will estimate causal effects with mediation (including the controlled direct effect, natural direct/indirect effects, and total effect)(Daniel, De Stavola, & Cousens, 2011).

20 Protocol/GCP non-compliance

The Principal Investigator should report any non-compliance to the trial protocol or the conditions and principles of Good Clinical Practice (GCP) to the CTR in writing as soon as they become aware of it.

The CTR will assess the nature and severity of any issues of non-compliance in accordance with their SOPs.

Minor changes in steroid dosing schedule due to patients' tolerance will not constitute a protocol noncompliance but should be recorded on the appropriate CRF.

21 End of Trial definition

The end of the trial is defined as the date of final data capture to meet the trial endpoints. Sponsor must notify the main REC of the end of a clinical trial within 90 days of its completion or within 15 days if the trial is terminated early.

22 Archiving

The TMF and TSF containing essential documents will be archived at an approved external storage facility for a minimum of 15 years. The CTR will send the TMF and TSFs to Sponsor for archiving. The Principal Investigator is responsible for archival of the ISF at site on approval from Sponsor. Essential documents pertaining to the trial shall not be destroyed without permission from the Sponsor.

23 Regulatory Considerations

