The aim of the study is to test the effectiveness of early IVIG treatment on time to recovery for autoimmune encephalitis. This will be a multicentre double-blind two-arm placebo-controlled randomised superiority trial of IVIG in adults with autoimmune encephalitis, incorporating an internal pilot study. The patients, their families, health care workers and the study team will all be blinded to protect against performance and ascertainment bias. A total of 356 adult participants with a diagnosis of autoimmune encephalitis, will be randomised from 50 UK based secondary and tertiary care centres in a ratio of 1:1 to receive either IVIG (2g/kg over 5 days) or placebo treatment (0.9% Saline). All participants will also receive methylprednisolone 1g daily intravenously for 5 days, followed by 60mg oral prednisolone daily for two weeks, and then taper regime (see section 1.4 for full dosing schedule).

The total trial duration is 73 months and the end of trial will be defined as last participant, last visit. There will be an internal pilot study comprising of 50 participants and several stop/go decision points at study month 10 and then at 6, 12, 18, and 24 months recruitment. Data collected will comprise of clinical data, questionnaires, and samples. GOSE assessments will occur fortnightly for the first 3 months and then monthly till 12 months post randomisation. Clinical assessment will occur at 2 weeks, 3 months and 12 months post randomisation, and annually. Participants will be followed up post study completion through the use of data linkage via NHS digital. This will constitute a separate study and will be funded and reported separately..

Cerebrospinal fluid (CSF) and serum IgG Fc glycosylation will be measured at baseline for all patients and compared with CSF and serum samples from 40 controls - patients who had a lumbar puncture for non-inflammatory causes such as migraine and idiopathic intracranial hypertension. Serum IgG glycosylation samples will be taken again at 3 months.

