11.12 Compliance

Any deviations from dosing schedule outlined in the trial protocol will be recorded on the appropriate CRF and will include at minimum new dose given, and reason for dose adjustment.

12 Sample Management

Participants will be asked if they are willing to consent to provide blood and/or CSF samples for the exploratory sub-studies. These samples will be used to explore the mechanisms by which IVIG produces benefit in patients. No samples collected for research (i.e. the exploratory sub-studies) will be used to inform primary or secondary trial outcome measures. The research samples (extra volumes of blood and/or CSF) will be collected at baseline (prior to IVIG treatment), 2 weeks and 3 months.

Samples will aim to be collected when the patient undergoes venepuncture / lumbar puncture as part of their clinical care at these time-points in their illness (to minimise unnecessary extra procedures).

As part of the consent process participants will be also be asked if any left-over CSF / blood remaining in the hospital laboratory after their initial clinical investigations (to determine if the patient had encephalitis) can be 'salvaged' and used to support the exploratory studies. These samples will particularly inform exploratory measurements for the 'acute' time-point of hospital admission. Local hospital laboratories will be informed of all participants who have consented for salvaged samples to be stored for the exploratory sub-studies.

Research samples (collected and salvaged) will initially be stored at hospital site in accordance with local policy. They will then be transported in batches to the University College London (UCL) Neuroimmunology and CSF Laboratory for central storage. Once received and logged by the lab at the University College London, samples will undergo exploratory measurements of inflammatory/host response markers (including glycosylation studies), and host biomarkers of brain damage at UCL. Some samples may also be transferred to the lab in University of Oxford to undertake detection / measurement for novel auto-antibodies. At the end of the trial, if consent is received samples will be sent to the University of Liverpool Ronald Ross building for storage in their biobank.

Figure 2 Sample Schedule and Quantities

Time	Acute	Baseline	2 weeks	3 months
CSF	5ml split into		4ml split into	
	4x1000μl and 2x500μl aliquots		3x1000μl and 2x500μl	
	1.proteome		aliquots	
	100μΙ		1.proteome	
	2.cytokines		100μΙ	

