12.1 Cytogenetics and Molecular Genetics

DNA will be extracted from participant's blood samples. See Figure 2 for amounts and vials required. DNA (EDTA sample) will be stored on patients for future genetic disease association studies. These future studies will look whether genetic polymorphism within patients, particularly within a region of the DNA called the Human Leukocyte Antigen (HLA) system, are linked to different clinical outcomes.

13 Trial procedures

Follow up assessments will place take place at weeks 2, 4, 6, 8, and 10, and then at months 3, 4, 5, 6, 7, 8, 9, 10, 11, and 12, 24, 36, and 48 post randomisation. All patients will complete the 2 weeks and 3 months follow up. The number of fortnightly assessments completed will depend on when they reach the primary endpoint and the number of monthly follow ups completed when they are recruited (see section 13.2 for time point cut-offs for assessments). Data collection be completed 3 months after the last patient is recruited.

Along with the main trial, there will be a mechanistic study looking at the role of glycosylation of the IgG Fc region. Samples will be taken at baseline and 2 weeks and then compared to samples from healthy volunteers who have undergone a lumbar puncture for non-inflammatory conditions. The CSF samples from healthy volunteers will be requested from the Walton Research CSF biobank. The biobank is managed by the Walton Centre NHS Foundation Trust, has full ethical approval from Wales REC4 and all samples are kept under the Human Tissue Authority License. The biobank request will be made independent of this trial and protocol. Full details of the mechanistic study can be found in section 19.

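### Section 19.3 fixes an unadjusted t-test for the non-randomised comparison of patients with 40 controls, so any age or sex difference related to glycosylation would be mixed with the disease effect

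*Protocol*

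**What the plan says.** Section 19.3 names the method for the patient-control comparison: "We will use independent samples t-tests to compare mean glycosylation at study entry between patients with autoimmune encephalitis and controls". It continues: "We will repeat this analysis comparing patients that are antibody positive against controls". No covariate is mentioned for either comparison. The same section does use analysis of covariance, but only between the randomised arms at 3 months, with baseline glycosylation as the covariate.

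Section 6 describes the controls: baseline CSF and serum glycosylation will be "compared with CSF and serum samples from 40 controls - patients who had a lumbar puncture for non-inflammatory causes", with migraine and idiopathic intracranial hypertension as examples. Section 13 calls the controls "healthy volunteers who have undergone a lumbar puncture for non-inflammatory conditions" and gives a source for one of the two fluids: "The CSF samples from healthy volunteers will be requested from the Walton Research CSF biobank". It adds: "The biobank request will be made independent of this trial and protocol". The source of the control serum is not stated.

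On the patients' side, section 12 says: "Research samples (collected and salvaged) will initially be stored at hospital site in accordance with local policy". Batches then go to a central laboratory. The schedule in section 13.1 collects patients' demographics at baseline. The protocol does not mention age or sex for the controls.

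**The concern.** Randomisation protects the comparison of IVIG with placebo. Nothing similar protects the comparison of patients with controls. The patients are adults aged 16 or over with acute encephalitis, from about 50 hospitals. The controls had a lumbar puncture for a different reason and were obtained by a different route. If the groups differ in age or sex, and if either is related to glycosylation, the difference in means contains that contribution as well as the disease effect. A t-test cannot separate the two.

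The first half of hypothesis 1 is that patients with this disease have aberrant IgG Fc glycosylation. Among the analyses named in section 19.3, only these t-tests set patients against people without the disease. A significant result would be read as support for that half, although part of the difference could come from who the controls are. The t-test is a stated choice of method, not detail left for the SAP.

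**Working it through.** **1. Is there a planned figure to reproduce?** No. Section 19.2 sizes only the comparison of randomised arms. It gives no power or detectable difference for patients against controls.

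**2. Inputs.**
- Controls: 40 (section 6).
- Patients: 228, the mechanistic sample size in section 19.2. Section 6 says baseline is measured in all patients, so 356 is shown as well.
- Antibody-positive patients: 68 (section 19.2, 30% of 228).
- SD: 13.3 (section 19.2). This was stated for the 3-month comparison of arms and is borrowed here.
- Spurious shift b from an age or sex imbalance: not in the documents. Assumed to be 0.1, 0.2 or 0.3 SD, that is 1.33, 2.66 or 3.99 units.

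**3. Standard error of the difference in means.** SE = SD × √(1/n₁ + 1/n₂).
- 228 v 40: 13.3 × √(1/228 + 1/40) = 2.28
- 356 v 40: 13.3 × √(1/356 + 1/40) = 2.22
- 68 v 40: 13.3 × √(1/68 + 1/40) = 2.65

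The 40 controls alone contribute 13.3/√40 = 2.10. More patients therefore barely change the SE, and they do not reduce bias.

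**4. False-positive rate when the true disease effect is zero.** With a two-sided 5% test, the rate is approximately Φ(−1.96 + b/SE) + Φ(−1.96 − b/SE). For 228 v 40:
- b = 1.33: b/SE = 0.58, rate about 9%
- b = 2.66: b/SE = 1.17, rate about 21%
- b = 3.99: b/SE = 1.75, rate about 42%

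The exact noncentral t calculation gives the following.

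| Comparison | 0.1 SD | 0.2 SD | 0.3 SD |
|---|---|---|---|
| 356 v 40 | 9% | 22% | 43% |
| 228 v 40 | 9% | 21% | 42% |
| 68 v 40 | 8% | 17% | 32% |

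**5. Does adjustment help?** A simulation with 4,000 runs per scenario used 228 v 40, no disease effect and one measured confounder. Two things were assumed: a correlation of 0.3 to 0.5 between confounder and glycosylation, and a group gap of 0.5 to 1.0 SD in the confounder. The t-test rejected in 13% to 82% of runs. A linear model containing the confounder rejected in 4.6% to 5.5%. This is the favourable case, because the confounder is measured without error and its effect is linear, as modelled.

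**6. What adjustment cannot reach.** If every patient sample is collected and stored one way and every control sample another, handling and group are the same variable. A regression then has no information with which to separate them.

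**The case against.** The strongest reply is that the comparison is peripheral. It belongs to the tertiary objectives, section 12 says that research samples do not inform primary or secondary outcome measures, and section 19.3 reserves the term main analysis for the randomised comparison at 3 months. All of that stands, and it limits the weight of the point.

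Second, the harm is assumed. The documents do not give the controls' age or sex, and do not say that glycosylation varies with either. The SD and mean in section 19.2 are for another comparison. This also stands: the percentages show how the test would behave under an imbalance, not that one exists.

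Third, a reader might infer that the controls are unmatched. The documents do not support that. The biobank request is made outside the protocol and may carry age or sex criteria. What can be said is that the protocol states none. The SAP, not shown here, might also add covariates, but it would then depart from the test that the protocol names.

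Fourth, a reader might infer that all control material comes from one biobank. That is documented for CSF only.

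Fifth, a reader might take a regression to solve differences in handling too. Adjustment for age and sex does not touch collection or storage, and shared plates remove only assay batch effects.

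**Conclusion.** The point holds as a cheap improvement to an exploratory analysis. Section 19.3 fixes an unadjusted test for a non-randomised comparison with separately obtained controls, and repeats it in antibody-positive patients. Any age or sex difference related to glycosylation would be mixed with the disease effect.

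The size is unknown. The figures of about 9%, 21% and 42% for 228 v 40 rest on assumed shifts of 0.1, 0.2 and 0.3 SD and on a borrowed SD of 13.3, and are illustrations only. A reader might go further and conclude that the mechanistic findings as a whole, or the trial's result, are compromised. The documents do not support that: the primary outcome and the 3-month analysis of covariance between arms do not use the controls.

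**What to change.** - In section 19.3, replace both t-tests with a linear regression of baseline glycosylation on patient/control status, adjusted for age and sex, with standard errors that allow unequal variances. Use the same model for the antibody-positive comparison.
- Obtain age and sex with the control samples, for CSF and for serum. State where the control serum comes from and whether controls are matched or selected on age or sex. Without these two fields, no later analysis plan can adjust for them.
- Describe the controls in one way. Section 6 has patients investigated for non-inflammatory conditions; section 13 has healthy volunteers.
- Mix patient and control samples across assay plates.
- Report differences in collection and storage that coincide with group as a limitation of the comparison.

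The cost is one model in place of a t-test, two extra data fields for 40 controls and a few degrees of freedom. Patients' demographics are already collected.

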23.1 CTA

This trial has Clinical Trials Authorisation (CTA) from the UK Competent Authority: MHRA.

Classification of whether any changes to the protocol is defined as a substantial amendment or not will be based on HRA guidance and sponsor assessment. All amendments will be reviewed by the TMG, and if necessary sponsor rep, for approval prior to being submitted, via IRAS and email, to REC, HRA, and if necessary the MHRA. The central trial team will alert all site trial teams and R&D departments once approval has been received for the amendment. The amendment history will be listed in the protocol and in the amendment log which is filed in the TMF.

23.2 Ethical and governance approval

This protocol will be submitted to a Research Ethics Committee (REC) that is legally "recognised" by the United Kingdom Ethics Committee Authority for review and approval. A favourable ethical opinion will be obtained from the REC before commencement of any study procedures (including recruitment of participants).

This trial protocol will be submitted through the relevant permission system for global governance review via the Health Research Authority (HRA).

Approval will be obtained from the host care organisation who will consider local governance requirements and site feasibility. The Research Governance approval of the host care organisation must be obtained before recruitment of participants within that host care organisation.

All substantial protocol amendments must be approved by the REC responsible for the study, in addition to approval by NHS Research and Development (R&D). Minor amendments will not require prior approval by the REC.

If the study is stopped due to adverse events or an urgent safety measure it will not be recommenced without reference to the REC responsible for the study.

The outcome of the study (e.g. completed) will be reported to the REC responsible for the study within 90 calendar days of study closure. In the event of the study being prematurely terminated a report will be submitted to the REC responsible for the study within 15 calendar days.

A summary of the results will be submitted to the REC responsible for the study within one year of completion of study closure.

23.3 Data Protection

The CTR will act to preserve participant confidentiality and will not disclose or reproduce any information by which participants could be identified, except where specific consent is obtained. Data will be stored in a secure manner and will be registered in accordance with the General Data Protection Regulation 2016/679. The data custodian for this trial is the Chief Investigator at Liverpool University (sponsor). There will be a joint data controller responsibility shared between Liverpool University (sponsor) and the CTR. The translational sample custodian for this trial is the University of Liverpool.

Participants will always be identified using their unique study identification number and any additional identifiers. This includes collection of NHS number (or equivalent – e.g. CHI number in Scotland), name and postcode to register and trace participants with NHS Digital. Any identifiable details will be stored separately to the clinical data. All data will be stored in the trial specific database detailed in section 18. The database will be held and maintained on secure servers hosted by Cardiff University. Access to the database is password protected and only granted to those relevant trial personal listed on the delegation log and appropriately trained. All paper CRFs will be held securely at site in locked cabinets and separately from any study documentation containing identifiable information.

23.4 Indemnity

ENCEPH-IG is sponsored by The University of Liverpool and will be co-ordinated by the CTR at Cardiff University. The Sponsor does not hold insurance against claims for compensation for injury caused by participation in a clinical trial and they cannot offer any indemnity. As this is an investigator-initiated study, The Association of the British Pharmaceutical Industry (ABPI) guidelines for patient compensation by the pharmaceutical industry do not apply. However, in terms of liability: NHS Trust and Non-Trust Hospitals have a duty of care to patients treated, whether or not the patient is taking part in a clinical trial, and they are legally liable for the negligent acts and omission of their employees. Compensation is therefore available in the event of clinical negligence being proven. The Sponsor does not accept liability for any breach in any other hospital's duty of care, or any negligence on the part of employees of hospitals. This applies whether the hospital is an NHS Trust or not.

Clinical negligence is defined as:

"A breach of duty of care by members of the health care professions employed by NHS bodies or by others consequent on decisions or judgments made by members of those professions acting in their professional capacity in the course of their employment, and which are admitted as negligent by the employer or are determined as such through the legal process".

The Sponsor has vicarious liability for the actions of its staff, when through the course of their employment they are involved in the design and initiation of a clinical trial, including but not limited to the authorship of the Clinical Trial Protocol. The University of Liverpool has appropriate insurance in place to cover this liability.

All participants will be recruited at NHS sites and therefore the NHS indemnity scheme/NHS professional indemnity will apply with respect to claims arising from harm to participants at site management organisations.

